7.2 Sample Size and Power

The primary efficacy endpoint is the absolute change in ppFEV₁ from baseline at Week 4. The primary null hypothesis to be tested is that the mean absolute change in ppFEV₁ from baseline at Week 4 is the same for the TC and TEZ/IVA treatment groups. The null hypothesis will be tested at a 2-sided significance level of 0.05.

Assuming a within-group SD of 7 percentage points and a 5% dropout rate at Week 4, a sample size of 50 subjects in each treatment group for a total of 100 subjects will have approximately 93% power to detect a difference of 5.0 percentage points for the mean absolute change in ppFEV₁ from baseline at Week 4 between the 2 treatment groups, based on a 2-sided 2-sample *t*-test at a significance level of 0.05 using the [REDACTED].

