9.3.1.4 Sensitivity Analysis

MMRM based on Multiple Imputation (MI)

An underlying assumption of the MMRM method is that data are missing at random. To minimize the amount of missing data, subjects who prematurely discontinue study drug treatment will continue to complete all scheduled study visits for spirometry and other efficacy assessments.

To assess the impact of missing data and the assumption that data are missing at random, a multiple imputation algorithm will be used if at least 10% of the subjects have missing changes in ppFEV₁ at Week 4 in any treatment group. Missing absolute change from baseline in ppFEV₁ assessments will be imputed starting from the first visit with missing values, for which all subsequent visits through Week 4 are also missing. For intermediate missing data, i.e., missing values that fall between two non-missing ones, it is reasonable to assume that they are missing at random and therefore will not be imputed. An MMRM analogous to that for the primary analysis of the primary endpoint will be applied to each imputed dataset and the relevant MI estimators will be reported. Details for the MI steps are presented in [Appendix D](#).

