Appendix D: Steps for Multiple Imputation

For the multiple imputation (MI) to be applied to the MMRM model for the primary efficacy endpoint, the following steps will be followed:

Imputation distribution

The imputation distribution for the missing absolute change from baseline in ppFEV₁ at visit t will be a normal distribution. All randomized subjects will be classified into one of three categories based on the following rules:

- Non-missing category: Subjects who have a ppFEV₁ assessment at Week 4 (i.e., subjects who have a non-missing absolute change from baseline in ppFEV₁ at Week 4).
- Missing category 1: Subjects with missing absolute change from baseline in ppFEV₁ at Week 4, who discontinued treatment because of adverse events, noncompliance with study drug, death, or physician decision, or because the subject refused further dosing or required prohibited medication.
- Missing category 2: Subjects who discontinued treatment for any reason not listed in Category 1 and have missing absolute change from baseline in ppFEV₁ at Week 4, or subjects who have completed 4 weeks treatment duration but are missing the absolute change from baseline in ppFEV₁ at visit Week 4

Imputation algorithm

We will use the following algorithm that relates the mean of the missing absolute change from baseline in ppFEV₁ at visit t to the missing categories defined above. The algorithm will be implemented within each treatment group as follows:

- Missing category 1: randomly draw a sample from the normal distribution(μ_{25}, σ^2), where μ_{25} is the 25th percentile of the non-missing absolute changes from baseline in ppFEV₁ at visit t and σ^2 is the sample variance estimated using the non-missing absolute changes at visit t .
- Missing category 2: randomly draw a sample from the normal distribution(μ, σ^2), where μ is the mean of the non-missing absolute changes from baseline in ppFEV₁ at visit t and σ^2 is the sample variance estimated using the non-missing absolute changes at visit t .

Analysis model

The complete MI method is described below:

- Form an “imputed dataset” by imputing missing values at each visit for those subjects who have a missing value at the visit and have all subsequent values missing. The appropriate normal distribution specified in the algorithm above will be used for each such subject, based on their category.
- Repeat this process K ($K=20$) times to form K imputed datasets.

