- Fit the same MMRM model to each imputed dataset to estimate the absolute change at Week 4.
- Combine the results from the K imputed datasets using the SAS procedure MIANALYZE to derive the MI estimator.

Let θ be the true treatment difference. Denote by $\tilde{\theta}_k$ the estimate of θ from the k^{th} imputed dataset, and the corresponding estimate of the variance is denoted by V_k . The MI estimator of θ , $\tilde{\theta}_{\text{MI}}$, is the average of the K individual estimates.

The estimated variance of $\tilde{\theta}_{\text{MI}}$ is a combination of the between- and within-imputation variability as follows: $V_{\text{MI}} = W + \left(1 + \frac{1}{K}\right)B$, where $W = \frac{1}{K} \sum_{k=1}^K V_k$ is the within-imputation variability and is $B = \frac{1}{K-1} \sum_{k=1}^K (\tilde{\theta}_k - \tilde{\theta}_{\text{MI}})^2$ is the between-imputation variance. The statistic $T = \frac{\tilde{\theta}_{\text{MI}} - \theta}{\sqrt{V_{\text{MI}}}}$ has an approximate t_V distribution, where $V = (K - 1)\left(1 + \frac{W}{B}\right)^2$.

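### Appendix D imputes from the same fixed arm estimates in all 20 datasets, so Rubin's variance for the sensitivity analysis omits their uncertainty: a minor flaw, usually about 2% of the standard error or less up to 20% missing

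*SAP*

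**What the plan says.** SAP 9.3.1.4 provides one sensitivity analysis of the primary endpoint: "a multiple imputation algorithm will be used if at least 10% of the subjects have missing changes" in ppFEV1 at Week 4 in either arm. SAP 9.3.1.3 rules out any supportive analysis, so this is the only planned check on the missing-at-random assumption.

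Appendix D works within arm and visit. Category 1 covers subjects who stopped for adverse events, noncompliance, death, physician decision, refusal of further dosing or need for prohibited medication. They are drawn from a normal distribution centred on the observed 25th percentile. Category 2, all other missing subjects, is centred on the observed mean. For both, sigma squared "is the sample variance estimated using the non-missing absolute changes at visit" t.

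On forming each dataset the appendix says: "The appropriate normal distribution specified in the algorithm above will be used for each such subject, based on their category". This is repeated K = 20 times, the MMRM is fitted to each dataset, and the variance of the pooled estimate "is a combination of the between- and within-imputation variability as follows": V = W + (1 + 1/K)B. The appendix contains no posterior draw and no bootstrap.

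**The concern.** Rubin's formula assumes that the imputed datasets differ for two reasons: the scatter of individual values, and uncertainty about the distribution they come from. Appendix D supplies only the first. The mean, percentile and variance are estimates from roughly 35 to 45 observed subjects per arm when 10 to 30% are missing, yet they are treated as known. B is therefore too small.

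At stake is the stated precision of the check. The analysis runs only when missingness is appreciable, and the omitted term grows roughly with the square of the missing share. A robustness analysis should not claim more precision than its method supports. The flaw would remain even if the choice of centre or the degrees of freedom were changed.

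**Working it through.** **Inputs.** From SAP 7.2: SD 7, 50 per arm, 5% dropout, difference 5.0, two-sided 0.05. From Appendix D: K = 20. Assumptions not in the documents: equal missing share f in both arms, missing completely at random and, first, no predictive covariate.

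**The plan's own figure.** Appendix D states no numerical result, so I reproduced the power. With 50 × 0.95 = 47.5 per arm, the SE is 7 × √(2/47.5) = 1.436, and 5/1.436 − 1.960 = 1.521. This gives 93.6% by the normal approximation and 93.1% by the noncentral t. The stated 93% reproduces.

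**Category 2, per arm** (n = 50, m = fn missing, σ² = 49):
- W = 49/50 = 0.980
- B as planned = mσ²/n²
- Term left out of B = (m/n)²σ²/(n − m)
- Planned variance = W + 1.05B
- Actual variance of the pooled mean = σ²/(n − m) + B/K

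| Missing | B planned | Omitted | Planned variance | Actual variance | SE ratio |
|---|---|---|---|---|---|
| 10% | 0.098 | 0.0109 | 1.083 | 1.094 | 0.995 |
| 20% | 0.196 | 0.0490 | 1.186 | 1.235 | 0.980 |
| 30% | 0.294 | 0.1260 | 1.289 | 1.415 | 0.954 |

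Planned B is (n − m)/n of what it should be, so it is short by exactly the missing share. The effect on the total SE is much smaller. At the planned 5% dropout the ratio is 0.999. Normal-theory coverage is 94.9%, 94.5% and 93.9% at 10%, 20% and 30%.

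If only one arm has 20% missing and the other none, the ratio is √[(1.186 + 0.980)/(1.235 + 0.980)] = 0.989.

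**Category 1, per arm.** The shifted draws inflate W to 0.980 × [1 + f(1 − f) × 0.6745²]. The actual variance is σ²/(n − m) × (1 + 0.857f²) + B/K. The SE ratios are 1.009 at 10%, 0.992 at 20% and 0.953 at 30%.

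**With the model the SAP fits.** An MMRM simulation used 8,000 trials per setting, an assumed Day 15 to Week 4 correlation of 0.6, and Monte Carlo error of about 0.008 on a ratio. Results are Rubin SE over empirical SD.

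| Category, baseline correlation, missing | As written | Variance and centre redrawn |
|---|---|---|
| 2, 0, 10% | 1.002 (coverage 95.1%) | 1.011 (95.3%) |
| 2, 0, 20% | 0.981 (94.2%) | 1.013 (94.9%) |
| 2, 0, 30% | 0.950 (93.5%) | 1.011 (94.9%) |
| 2, 0.4, 10% | 1.019 | 1.032 |
| 2, 0.4, 20% | 1.005 | 1.036 |
| 1, 0, 10% | 1.007 | 1.023 |
| 1, 0.4, 10% | 1.027 | 1.044 |
| 1, 0, 20% | 0.996 | 1.043 |

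A simpler baseline-adjusted simulation of the Week 4 change, all in Category 2, covered correlations of 0 to 0.4. The ratio was about 0.99 to 1.01 at 10% and 20% missing, and 0.95 to 0.98 at 30%. With a correlation of 0.3 to 0.4, the shortfall at 30% was 2 to 3%.

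**Size of K.** The Monte Carlo SD of the estimated difference is √(2B/K). At K = 20 with the planned B it is √(2 × 0.098/20) = 0.099 at 10% missing and √(2 × 0.196/20) = 0.140 at 20%. At K = 200, using B with the omitted term restored (0.109 and 0.245), it is 0.033 and 0.049.

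**The case against.** The strongest reply is that the planned interval need not be too narrow at all. Appendix D refits the MMRM, which adjusts for baseline ppFEV1 and age, while the draws ignore baseline and Day 15. That mismatch pushes Rubin's SE up. A reader might infer from the closed form that the interval is always too narrow, or even narrower than one from the observed subjects alone, which would be impossible for draws around the arm's own mean. The documents do not support that in general. In a baseline-adjusted check at an assumed correlation of 0.3, the planned SE exceeded the observed-only SE: 1.425 against 1.412 at 10% missing, and 1.504 against 1.498 at 20%. The documents give no such correlation, so the direction of the net error is open at these levels. This stands. It does not validate the method, because the offset is accidental and of unknown size, and it no longer suffices at 30% missing.

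It is also fair that the analysis may never run. Planned dropout is 5%, subjects who stop treatment keep attending visits (Protocol 9.1.5.2), and most named reasons for stopping lead to Category 1, where the SE is about right up to 20% missing. Finally, the redraw moves a Category 1 SE from about right to about 3 to 7% too large in the baseline-adjusted check (1 to 4% in the MMRM simulation). At 10 to 20% missing, that can exceed the error being removed. This cost is real and must be stated with the fix. Counting B/K in Rubin's formula, as the SAP does, covers the Monte Carlo noise but does not reduce it.

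**Conclusion.** The point holds as a minor technical flaw. The imputation in Appendix D is improper, and nothing elsewhere in the SAP repairs it. The quantity affected is the interval for the Week 4 treatment difference in a conditional sensitivity analysis. The primary MMRM imputes nothing, and the expected value of the pooled estimate does not change.

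At the 10% trigger the effect is negligible. It becomes material only near 30% missing, where Category 2 coverage falls to about 93 to 94%; without predictive covariates, the Category 1 SE is also about 5% too small there by the closed form. These sizes rest on SD 7, 50 per arm, equal missingness completely at random and assumed correlations. Missingness confined to one arm roughly halves them. No conclusion about a 5-point difference would turn on this.

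**What to change.** In Appendix D, add a step before each of the K imputations, within arm and visit:
- draw σ*² = (n_obs − 1)s²/χ²(n_obs − 1) and μ* from N(observed mean, σ*²/n_obs), then impute Category 2 from N(μ*, σ*²);
- impute Category 1 from N(μ25*, σ*²), with μ25* the 25th percentile of a bootstrap resample of that arm's observed changes.

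A bootstrap of the observed changes can supply all three quantities instead. Keep the categories and the combining rule. Separately, raise K from 20 to at least 200.

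The cost is one or two SAP sentences and a few lines of SAS before database lock, with no new data and negligible computing time. In the MMRM simulation without baseline correlation, the Category 2 SE rises from 1.484 to 1.500 at 10% missing (+1.1%) and from 1.549 to 1.600 at 20% (+3.3%). The SAP should also say that an interval dominated by Category 1 becomes mildly conservative.

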9.3.1.2 Primary Analysis

The primary analysis will be performed using a mixed-effects model for repeated measures (MMRM) with the absolute change from baseline at Day 15 and Week 4 as the dependent variable. The model will include treatment group, visit, and treatment-by-visit interaction as fixed effects, with continuous baseline ppFEV₁, and age at screening (<18 versus ≥18 years of age) as covariates. The model will be estimated using restricted maximum likelihood.

Denominator degrees of freedom for the F -test for fixed effects will be estimated using the Kenward-Roger approximation². An unstructured covariance structure will be used to model the within-subject errors. If the model estimation does not converge, a compound symmetry covariance structure will be used instead. Conditional on the observed data and covariates, missing data will be assumed to be missing at random; consequently, no imputation of missing data will be performed.

The primary result obtained from the model will be the estimated treatment difference at Week 4. The adjusted means with 2-sided 95% confidence intervals and 2-sided P values will be provided. Furthermore, the treatment difference at each post-baseline visit obtained from the model will also be provided.

The adjusted mean (with SE) obtained from the MMRM analysis at each post-baseline visit up to Week 4 will be plotted by treatment group.

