9.3.1.3 Supportive Analysis

There will be no supportive analysis for the primary efficacy endpoint.

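### SAP Appendix D imputes missing Week 4 ppFEV1 change without the subject's Day 15 change, so the only planned check on missing at random can drift from the primary analysis for the wrong reason (minor, cheap to repair)

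*SAP*

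**What the plan says.** The primary analysis (SAP 9.3.1.2) is a mixed model for repeated measures (MMRM) "with the absolute change from baseline at Day 15 and Week 4 as the dependent variable". It has treatment, visit and their interaction, baseline ppFEV1 and age group, an unstructured covariance, and a MAR assumption conditional on observed data and covariates. A subject with Day 15 but no Week 4 value therefore informs the Week 4 estimate through Day 15.

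SAP 9.3.1.3 states: "There will be no supportive analysis for the primary efficacy endpoint". SAP 9.3.1.4 gives one sensitivity analysis, with the aim "To assess the impact of missing data and the assumption that data are missing at random". It runs only "if at least 10% of the subjects have missing changes in ppFEV₁ at Week 4 in any treatment group".

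Appendix D sets the method. "The algorithm will be implemented within each treatment group as follows": for Category 1 (treatment stopped for adverse events, noncompliance, refusal and similar reasons) the centre of the normal draw "is the 25th percentile of the non-missing absolute changes from baseline in ppFEV₁ at visit" t. For Category 2 it "is the mean of the non-missing absolute changes from baseline in ppFEV₁ at visit" t. Both use the sample variance of the observed changes at that visit. Category 2 covers those who stopped for other reasons and also "subjects who have completed 4 weeks treatment duration but are missing the absolute change from baseline in ppFEV₁ at visit Week 4". The same MMRM is then fitted to each of K=20 filled datasets and the results are pooled.

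**The concern.** Neither draw uses the subject's Day 15 change, baseline ppFEV1 or age group. A Category 2 subject who finished treatment and lacks only Week 4 will usually have a Day 15 value. If that value was poor, the primary model predicts a below-average Week 4 change, whereas Appendix D assigns a draw around the arm average. Each arm's imputed mean is then right only if loss is unrelated to Day 15 response within that arm. That is a stronger assumption than the one the analysis is meant to examine. Refitting the MMRM does not restore the information, because Week 4 is already filled with values independent of Day 15.

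Two things follow. A gap between the check and the primary result may say nothing about departure from MAR. And Category 1, meant as the pessimistic case, can lose its penalty when poor Day 15 responders are the ones lost. The Category 1 penalty itself is a deliberate departure from MAR and is not criticised here.

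**Working it through.** **Inputs from the documents** (SAP 7.2, 9.3.1.4, Appendix D): 50 per arm, SD 7, difference 5.0, 5% dropout, trigger at 10% missing in an arm (5 of 50), K=20.

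**Assumed, because the documents are silent:** Day 15/Week 4 correlation ρ of 0.3, 0.5 or 0.7, and which subjects are lost.

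**1. The plan's own figure.** With 50 × 0.95 = 47.5 per arm, the noncentrality is 5/(7 × √(2/47.5)) = 3.48, and the two-sided t-test power is 93.1%. The stated 93% reproduces.

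**2. Category 2 by hand.** If k of 50 in an arm are lost, the arm mean is off by (k/50) × ρ × 7 × gap, where gap is the Day 15 difference in SDs between observed and lost subjects. The mean of the lowest third of a normal distribution is -1.09 SD, so gap = 1.09 × 50/(50 - k).
- k = 5: gap 1.21, shift 0.10 × 7 × 1.21 × ρ = 0.85ρ.
- k = 2: gap 1.14, shift 0.04 × 7 × 1.14 × ρ = 0.32ρ.
- 5 TC and 2 control: 0.53ρ = 0.16 / 0.27 / 0.37.
- 5 TC and 0 control: 0.85ρ = 0.25 / 0.42 / 0.59.

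**3. Simulation of the full procedure.** 2,000 trials per cell; two-visit MMRM with unstructured covariance, baseline and age covariates; assumed baseline correlation with change -0.2, 30% under 18, age effect 1 point. Entries are Appendix D minus MMRM, in percentage points.

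| Category, TC/control missing, loss | ρ 0.3 | ρ 0.5 | ρ 0.7 |
|---|---|---|---|
| 2, 5/2, lowest third | +0.16 | +0.25 | +0.36 |
| 2, 2/5, lowest third | -0.16 | -0.26 | -0.36 |
| 2, 5/0, lowest third | +0.25 | +0.41 | +0.58 |
| 2, 5/2, lowest half | +0.11 | +0.19 | +0.26 |
| 2, 5/5, lowest third | 0.00 | 0.00 | 0.00 |
| 2, 5/2, random | 0.00 | +0.01 | -0.01 |
| 1, 5/0, random | -0.46 | -0.46 | -0.45 |
| 1, 5/0, lowest third | -0.21 | -0.04 | +0.13 |
| 1, 5/2, random | -0.27 | -0.28 | -0.28 |
| 1, 5/2, lowest third | -0.12 | -0.01 | +0.10 |

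Simulation error of these differences is 0.001 to 0.007, and the hand figures agree.

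**4. Category 1 by hand.** The penalty per subject is 0.6745 × 7 = 4.72 points. For 5 of 50 this is -0.47. Adding the Day 15 shift of 0.85ρ gives -0.22 / -0.05 / +0.12, close to the simulated -0.21 / -0.04 / +0.13.

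**5. Scale.** The standard error is about 1.41, so the 5-versus-2 shift is 0.16/1.41 = 0.11 to 0.36/1.41, about 0.25, standard errors.

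**6. How often the check runs.** If 5% of Week 4 values are missing, P(5 or more of 50) = 0.104 per arm and 1 - (1 - 0.1036)² = 0.196 for at least one arm. At 3% missing the latter is 3.3%; at 2% it is 0.6%. Given a trigger at 5% missing, the larger and smaller counts average 5.5 and 2.3, and a gap of 5 or more occurs in 20%. Exactly 5 versus 2, in either direction, is 17.5% of triggers, so it is an illustration and not a typical outcome.

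**The case against.** The strongest reply concerns consequence. A visible shift needs the 10% trigger, unequal loss between arms, loss related to Day 15, and Day 15 observed. The plan works against these. Protocol 9.1.5.2 keeps subjects who stop drug in the visit schedule, SAP Appendix A accepts spirometry from Days 23 to 43 as Week 4, the open-label study is offered to those who complete the Week 4 Visit (Protocol 9.1.4), and subjects should not be told their spirometry results (Protocol 10.7.1). Symptoms could still drive loss, but the mechanism is assumed. All of this stands, and it makes the point minor.

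A second reply is that a repaired Category 2 only repeats the primary analysis if every missing subject is in Category 2. That is true. Agreement is what a MAR draw should show; departures should come from the stated penalty.

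A reader might infer that Appendix D favours TC. The documents do not support this: the sign follows whichever arm loses more poor Day 15 responders.

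A reader might also count trials in which the two analyses disagree at p<0.05 and treat these as harm. With 5 TC and 2 control lost from the lowest third, disagreement at a true difference of 5.0 is 1.3% to 2.6%, nearly always with only Appendix D significant. In a simpler model without covariate effects, purely random 5-versus-2 loss already gives about 1.5% to 2%, and the reversed counts give mostly the opposite disagreement. At the planned effect, most of that rate cannot be put down to the missing Day 15 term.

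**Conclusion.** The point holds as a minor weakness in the sensitivity analysis. Appendix D leaves out observed information that the primary model uses, and each arm's Category 2 mean then rests on more than MAR. In the treatment difference the error cancels when both arms lose similar numbers in the same way, so it would be wrong to call the Category 2 difference invalid whenever loss depends on Day 15.

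Under loss from the lowest Day 15 third and correlations of 0.3 to 0.7, the shift is 0.16 to 0.36 points in either direction at 5 versus 2 missing. The Category 1 penalty for 5 versus 0 falls from about -0.46 to between -0.21 and +0.13, so the stress test can be milder than intended. These sizes depend on the assumed correlation and loss pattern. The primary test and its conclusion are not affected, and the documents give no ground for saying otherwise.

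**What to change.** Amend Appendix D before database lock, which SAP Section 4 allows.

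1. Draw each missing Week 4 change from a normal regression on treatment, observed Day 15 change, baseline ppFEV1 and age group, fitted to subjects with both visits. Draw the regression parameters from their posterior for each of the K=20 imputations. If Day 15 is also missing, draw it first from treatment, baseline and age group.
2. Category 2: keep this draw, which reproduces MAR.
3. Category 1: after the draws, subtract the existing own-arm penalty (mean minus 25th percentile at that visit), so that departures from MAR come only from it.
4. Keep the two categories, K, the MMRM and MIANALYZE.

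In simulation with Day 15 observed, Category 2 then lies within 0.005 points of the MMRM in every cell. Category 1 gives -0.44 to -0.46 for 5 TC and 0 control, and -0.27 to -0.28 for 5 and 2, whether loss is random or from the lowest third. The branch with Day 15 also missing, and mixtures of the two categories, were not simulated. Day 15 is the omission that matters: with no baseline or age effect, conditioning on it alone matches the full regression to within 0.005. Baseline and age group are included to match the MMRM.

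Cost: one appendix edit and a little programming, with no new data and no change to the primary analysis. The sensitivity estimate may be slightly less favourable to TC: for 5 TC and 0 control, all Category 1 from the lowest third, -0.44 to -0.46 from the MMRM instead of -0.21 to +0.13.

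### SAP Appendix D: the printed multiple-imputation degrees of freedom do not match the printed variance (negligible effect), and they have no small-sample limit, which leaves the sensitivity-analysis interval about 1.4–1.6% too narrow

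*SAP*

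**What the plan says.** SAP 9.3.1.2 analyses the primary endpoint with a mixed model for repeated measures, in which degrees of freedom "for fixed effects will be estimated using the Kenward-Roger approximation". SAP 9.3.1.4 adds one sensitivity analysis for missing data: "a multiple imputation algorithm will be used if at least 10% of the subjects have missing changes in ppFEV₁ at Week 4" in either arm.

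Appendix D gives the steps:
- "Repeat this process K ($K=20$) times to form K imputed datasets".
- Refit the primary mixed model to each imputed dataset.
- "Combine the results from the K imputed datasets using the SAS procedure MIANALYZE to derive the MI estimator".

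It then prints the pooled variance as V_MI = W + (1 + 1/K)B, where W is the within-imputation and B the between-imputation variance. The standardized estimate "has an approximate t_V distribution" with V = (K − 1)(1 + W/B)². No complete-data degrees of freedom appear in the formula or in the instruction to use MIANALYZE.

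**The concern.** There are two separate points about one line of Appendix D.

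1. The factor (1 + 1/K) multiplies B in the variance but is missing from the degrees of freedom. The two lines cannot both be right.
2. V treats W as known without error, so it grows without limit as B shrinks. Each fit uses Kenward-Roger degrees of freedom, but pooling discards them. An analysis with imputed values can then claim far more degrees of freedom than the same model would have with complete data.

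What is at stake is the error bars of the only prespecified check of the missing-at-random assumption; SAP 9.3.1.3 plans no supportive analysis. A check on the primary result should not use a more favourable reference distribution than the primary analysis does. The point estimate and the primary analysis are unaffected.

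**Working it through.** **Inputs from the documents.** K = 20, so 1 + 1/K = 1.05 and K − 1 = 19 (Appendix D). "Assuming a within-group SD of 7 percentage points and a 5% dropout rate at Week 4", with 50 subjects per arm (SAP 7.2).

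**The plan's own figure.** The SAP prints no degrees of freedom or interval width for this analysis. Its stated design figure is power of about 93% for a 5.0-point difference. A two-sample t-test with 50 × 0.95 = 47.5 evaluable per arm and SD 7 gives 93.1%, so the inputs reproduce.

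**Assumptions not in the documents.**
- Complete-data degrees of freedom ν₀ = 92 to 96: about 100 subjects less the model terms.
- The ratio r = B/W. In a simplified two-arm Week 4 comparison with m of n values imputed per arm, B ≈ 2mσ²/n² and W ≈ 2σ²/n, so r ≈ m/n. That is about 0.10 at 10% missing and 0.20 at 20%. Simulating the Appendix D draws gave median r of 0.092–0.096 and 0.180–0.190, depending on the mix of the two missing categories.

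**Step 1: the degrees of freedom that match the printed variance.** Take B with K − 1 degrees of freedom and W as known, and match moments of V_MI:

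V_MI² ÷ {[(1 + 1/K)B]² / (K − 1)} = (K − 1)[1 + W/((1 + 1/K)B)]².

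The printed V lacks the factor.

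**Step 2: size of the slip at r = 0.10.**
- Printed: 19 × (1 + 1/0.10)² = 19 × 121 = 2,299; t quantile 1.9610.
- With the factor: 19 × (1 + 1/0.105)² = 2,104; t quantile 1.9611.
- The interval widens by about 0.005%.

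**Step 3: small-sample degrees of freedom (Barnard-Rubin) at r = 0.10.**
- γ = 1.05r/(1 + 1.05r) = 0.105/1.105 = 0.095.
- ν_obs = [(ν₀ + 1)/(ν₀ + 3)] ν₀ (1 − γ). For ν₀ = 96: (97/99) × 96 × 0.905 = 85.1.
- Combined: 1/(1/2,104 + 1/85.1) = 81.8; t quantile 1.989.
- Narrowing: 1 − 1.9610/1.9894 = 1.43%. With ν₀ = 92 it is 1.49%.

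**Step 4: in ppFEV₁ points at r = 0.10.** W = 2 × 49/50 = 1.96 and V_MI = 1.96 × 1.105 = 2.166, so the standard error is 1.472. The half-width is 2.886 with the printed V and 2.928–2.930 with the small-sample rule, a change of 0.042–0.044.

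**Results (ranges are for ν₀ = 96 and 92).**

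| r | Printed V | With factor | Small-sample | Effect of factor | Narrowing | Half-width change |
|---|---|---|---|---|---|---|
| 0.096 | 2,476 | 2,266 | 79–82 | 0.005% | 1.42–1.48% | 0.042–0.043 |
| 0.10 | 2,299 | 2,104 | 78–82 | 0.005% | 1.43–1.49% | 0.042–0.044 |
| 0.19 | 745 | 687 | 68–70 | 0.014% | 1.56–1.63% | 0.048–0.050 |
| 0.20 | 684 | 631 | 67–69 | 0.015% | 1.57–1.64% | 0.048–0.051 |

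If the small-sample distribution is the right reference, a nominal two-sided 0.05 test runs at about 0.053–0.054.

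**Step 5: dependence on the comparator.** A plain Satterthwaite combination that gives W its own 92–96 degrees of freedom still shows 0.9–1.1% narrowing. The direction does not depend on choosing Barnard-Rubin; the size does.

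**Step 6: simulated coverage of the 95% interval.** The setting is the simplified two-arm model with equal missingness, draws from the observed mean and variance, K = 20 and ν₀ = 96. Repeated runs gave, at 10% missing, 94.4–94.6% with the printed V and 94.8–95.0% with the small-sample rule. At 20% missing they gave 94.0–94.3% and 94.4–94.6%. The remaining shortfall at 20% has another source: Appendix D draws from fixed estimates of the mean and variance, which leaves the pooled standard error about 2.8% below the empirical one.

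**The case against.** The case against giving this weight is strong, and most of it stands.

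- **The one true slip does nothing visible.** A reader might infer that the missing (1 + 1/K) causes the 1.4–1.6% narrowing. It does not: more than 99% of that comes from the absent small-sample limit.
- **The part with an effect is a choice of method.** Rubin's classical degrees of freedom have no complete-data limit either, and the SAP promises none. Calling its absence an error goes too far. What remains is an inconsistency of approach with the Kenward-Roger primary analysis.
- **It is tempting to say that the sensitivity analysis has no small-sample correction at all.** The documents do not support that. The same mixed model is refitted to each imputed dataset, so Kenward-Roger applies within each fit; only the pooled reference distribution lacks a limit.
- **The printed slip may never reach the output**, because MIANALYZE does the combining. The documents do not say how its degrees of freedom are set or whether a complete-data value is supplied. That leaves the SAP silent on the input that matters, which is a reason to state it.
- **Practical weight is low.** The analysis needs 10% missing in an arm against 5% assumed dropout, discontinued subjects are still followed, and it lies outside the testing hierarchy. A conclusion about significance could change only for a P value within a few thousandths of 0.05.

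**Conclusion.** The concern holds as two separate statements.

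1. The printed V is inconsistent with the variance printed beside it. This is wrong as written, and its effect is about 0.005–0.014% of interval width.
2. The pooled degrees of freedom, about 750–2,500 at 10–20% missing, ignore a sample of about 100. Against Barnard-Rubin the interval is about 1.4–1.6% too narrow, or 0.04–0.05 points on a half-width near 2.9–3.0. Supplying the limit is a cheap improvement.

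The size rests on assumed complete-data degrees of freedom of 92–96 and on B/W from a simplified Week 4 model. Over a wider range of missingness, at 96 degrees of freedom, median narrowing was about 1.37% at 6% missing and 1.66–1.71% at 30%. The narrowing is a ratio of t quantiles and should not be read as the whole calibration error. The limit improves coverage but does not fully restore 95% at 20% missing. Severity is minor, and nothing here bears on the primary result.

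**What to change.** In Appendix D:

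- Replace V by (K − 1)[1 + W/((1 + 1/K)B)]², so that it matches V_MI.
- State that inference uses the Barnard-Rubin small-sample degrees of freedom, built from that V and the complete-data degrees of freedom.
- State that the Kenward-Roger degrees of freedom for the Week 4 treatment contrast are passed to the combining step as the complete-data value. Since there are 20 fits, also say how one value is taken from them (for example, the smallest).

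The cost is one formula, one sentence and one input to the pooling step. Design, data collection and point estimates do not change. The downside is a slightly wider interval, by about 1.4–1.7%, in an analysis that may not be triggered. This change does not deal with the draws from a fixed mean and variance, which would need a separate change to the imputation step.
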